Our hypothesis is that infections cause inflammation and LN fibrosis. A particularly innovative feature of this protocol is the ability to characterize the infectious burden of an individual using the new “Pathseq” technique developed by [name]. This involves deep sequencing of RNA and DNA fragments (ranging in size from ~100-1000 bases) in plasma to obtain an overall quantitative and qualitative measure of the viral, bacterial, fungal, and parasite microbial burden as well as helminth burden in an individual. This approach differs from standard microbiome approaches such as bacterial 16s rDNA sequencing or virus purification and sequencing as it is sequence agnostic and takes advantage of the fact that circulating nucleic acids are typically highly fragmented to provide information about the “circulating microbiome”. Nucleic acids from all microbes, worms and even food are readily detected using our PathSeq approach, and likely represent recent history of non-human genomic burden as circulating nucleic acids are typically very short-lived.


were completely concordant, providing further validation of this technique to assess the microbial burden. Also of importance, the pattern is remarkably stable over a 9-month period, suggesting patterns that emerge can be viewed as a chronic pattern of microbial burden.

In **Fig. 8** we show the PathSeq result from 10 Ugandan HIV+ individuals collected over 9 months after initiating ART. The y-axis shows relative read frequency. We noted two distinct patterns of infectious burden. The plasma of the 6 participants in the upper row of **Fig. 8** predominantly contained bacterial nucleic acids from the Proteobacteria family whereas in the lower row of 5 participants GBV-C virus and helminthic nucleic acids predominated. Each group exhibited a markedly different cytokine profile after 9 months of ART. Infection with primarily proteobacteria was associated with higher levels of the pro-inflammatory cytokines IL-6 and TNF, and sCD14 (a marker of bacterial translocation) and inversely correlated to IL-17 and MIP1b. In contrast, participants with predominantly helminthic and GBV-C nucleic acids had exactly the opposite cytokine profile after 12 months of ART; high levels of IL-17 and MIP1b and low levels of IL-6 and sCD14.

[figure not shown]

Fig 8: Two patterns of microbial burden identified over 9 months of FU.

Pathseq is a tool to provide quantitative information about the chronic infectious burden of an individual that we can use to investigate relationships between infections, LN inflammation and fibrosis, and vaccine responses. There is evidence that such relationships likely exist. For example, in a recent HIV vaccine study in Africa, participants infected with *S. mansoni* had significantly lower titers of antibodies than those who were not (31). Combining Pathseq with our analyses of antibody titers, cytokine profiles before and after vaccination, and our analysis of LN architecture will provide important information about the role of the local infectious burden as a determinant of immune response to vaccination.

We show in our preliminary data that chronic IA, inflammation and damage to LN architecture in HIV negative Ugandans correlates with neutralizing antibody titers after YFV. The demonstration of increased levels of TGF β at baseline along with an IL-10 and IL-17 response after YFV suggests helminthic infections may be contributing to abnormal vaccine responses and supports our hypothesis that endemic infections may affect immune responses to vaccination. We demonstrate the ability to characterize infectious burden, and while this does not define the entire life history of pathogen exposure, it is surprisingly stable over time allowing us to use this as a record of infectious exposures. We now propose to build on these initial observations by conducting a controlled study with YFV in both Uganda and the USA to better understand how endemic infections and environmental factors may affect innate and adaptive immune responses to vaccination and better define how these factors might inhibit immune mechanisms and components that lead to sustained immunity. Our data raise several important questions, including 1) what is causing the generalized IA, 2) how does systemic IA lead to a local process of collagen formation in the FRCn, 3) how are antigen specific CD4 and CD8 T cells affected by loss of the FRCn, 4) Why are their fewer TFH in Ugandans, 5) does the frequency and function of TFH cells in Ugandans affect the magnitude and durability of the vaccine response, 6) does relative T cell depletion in this population limit recall responses, and 7) does the mucosal environment, in particular in GALT infections from helminths or enteric pathogenic bacteria, affect the magnitude or durability of immune responses? Our hypothesis is that infections other than HIV can cause LN inflammation and collagen damage to the FRCn which will lead to CD4 T cell depletion and impaired vaccine responses.

We will address this hypothesis by giving YFV to a group of otherwise healthy people in Uganda and Minnesota and we will systematically collect blood, and LN specimens before and after YFV. Our approach is feasible as we have already demonstrated that we can conduct a trial of this nature at the

Joint Clinical Research Center in Kampala, Uganda where we have collected LN and blood samples at multiple time-points throughout several protocols, including the YFV study described above. In the past 8 years, we have enrolled over 105 participants in HIV pathogenesis and vaccine studies at the JCRC who have contributed 228 LN biopsies. Importantly, we now have capacity to perform leukapheresis at the JCRC in Uganda as they recently acquired the equipment and expertise to perform this procedure. We have demonstrated the ability to process, maintain, and ship specimens from the Uganda site to Minnesota. In Minnesota, we have enrolled 170 HIV+ and 100 HIV- people in multiple pathogenesis and interventional trials where we have collected 413 LNs, 1657 PBMC and plasma samples from these individuals. We now propose to collect the relevant specimens before and after YFV to apply state-of-the-art technologies to address fundamental question about how and why vaccine responses are limited in some populations.

2.3 RISK/BENEFIT ASSESSMENT

2.3.1 KNOWN POTENTIAL RISKS

Risks Associated with Yellow Fever Vaccine

Common side effects:

- Injection site reaction, including erythema and pain at injection site
- Headache
- Fever
- Myalgia
- Malaise

Rare side effects:

Severe Allergic Reactions

Severe allergic reactions (e.g., anaphylaxis) may occur following the use of Stamaril or YF-VAX, even in individuals with no prior history of hypersensitivity to the vaccine components. Appropriate medical treatment and supervision must be available to manage possible anaphylactic reactions following administration of the vaccine.

Yellow fever vaccine-associated viscerotropic disease

Age greater than 60 years is a risk factor for yellow fever vaccine-associated viscerotropic disease (YEL-AVD) which may present as non-specific multi-organ system failure or can be similar to fulminant yellow fever caused by wild-type yellow fever virus, with liver failure and internal bleeding, leading to death. Available evidence suggests that the occurrence of this syndrome may depend upon undefined host factors, rather than intrinsic virulence of the yellow fever strain 17D vaccine, based on characterization of vaccine viruses isolated from individuals with YEL-AVD. YEL-AVD has been reported to occur only after the first dose of yellow fever vaccine; there have been no reports of YEL-AVD following booster dose. The decision to vaccinate individuals 60 years of age and older needs to weigh the risks and benefits of vaccination and the risk for exposure to yellow fever virus.

Yellow fever vaccine-associated neurotropic disease

Age greater than 60 years and immunosuppression are risk factors for post-vaccinal encephalitis, also known as yellow fever vaccine-associated neurotropic disease (YEL-AND). Almost all cases of YEL-AND have been in first-time vaccine recipients. The decision to vaccinate individuals 60 years of age and older

and immunosuppressed individuals needs to weigh the risks and benefits of vaccination and the risk for exposure to yellow fever virus.

Risks Associated with Protocol Directed Procedures:

Lymph Node Biopsy

The risks of the lymph node biopsy are bleeding, infection, seroma, and scarring. Any participant who develops a seroma will have it drained with a syringe in the clinic. These complications are rare. All post-operative and post-biopsy care will be provided by study nurses. Participants will be monitored for a minimum of 4 hours post-surgery prior to being allowed to return home. If complications occur, the participant will be seen immediately by a qualified surgeon.

Leukapheresis

The risks of the apheresis process include bruising and/or bleeding in the arms when needles are placed for the apheresis; a reaction to the drug used as an anticoagulant during the procedure, citrate; and loss of blood, especially platelets. Rarely, veins cannot be found to insert the needles a catheter must be placed in a large neck vein to collect the cells.

Blood Draw

Events associated with venipunctures include discomfort, slight bruising, bruising, bleeding, lightheadedness, fainting, infection at the venipuncture site, nausea, anxiety and swelling at the venipuncture site.

2.3.2 KNOWN POTENTIAL BENEFITS

There are no anticipated benefits to participants on this study.

There is a potential for societal benefit, as this study could demonstrate the need for alternative vaccine constructs and other strategies to improve vaccine efficacy rates.

2.3.3 ASSESSMENT OF POTENTIAL RISKS AND BENEFITS

There is a low possibility of side effects. There are no potential benefits besides findings from the proposed research could lead to a clearer understanding of the requirements for inducing durable protective immunity.

3 OBJECTIVES AND ENDPOINTS

OBJECTIVES	ENDPOINTS	JUSTIFICATION FOR ENDPOINTS
Primary		
To determine the relationship between endemic infections, immune activation (IA), T cell zone (TZ) fibrosis with loss of the fibroblastic reticular cell network (FRCn), CD4 and CD8 T cell subsets and the magnitude and durability of neutralizing antibody response to YFV in a cohort shown to have elevated IA,	Peak titer of neutralizing antibody to yellow fever vaccination	The primary analysis endpoint is the peak titer of neutralizing antibody. We believe that there will be significant differences in the peak titer and durability of titers between the two groups.

OBJECTIVES	ENDPOINTS	JUSTIFICATION FOR ENDPOINTS
a damaged FRCn, and pan T cell depletion and a cohort that does not.		
Secondary		
To determine predictors of levels of neutralizing antibodies	
 1. Measures of T cell zone fibrosis (collagen and desmin) 2. Measures of past and present infection (pathseq, molecular analyses of helminth infection and serum antibody studies) 3. Measures of immune activation (Ki67+ and CD69 + cells) 4. Measures of systemic and lymphatic inflammation (plasma cytokines, frequency of TGFβ+ and TNF+ cells in lymphoid tissues). 5. Changes in T cell number and function 	We believe the reason that titers will be different is that inflammation from endemic infections alters the architecture and therefore the function of the lymphatic tissues which results in less antibody being made. With these secondary endpoints we will measure these potential predictors.
Tertiary/Exploratory		
To determine the impact of LN fibrosis on specific T cell populations including T follicular helper cells and antigen specific T cells.	
 1. Histologic analyses of lymphoid tissues for T follicular helper cells and B cells. 2. Size and change to the frequency of yellow fever antigen specific CD4+ T cell population. 	We have shown that lymphatic tissue fibrosis causes depletion of CD4 and CD8 + T cells however we have never examined the impact on highly specific subsets.

4 STUDY DESIGN

4.1 OVERALL DESIGN

The primary aim of this study is to determine the difference between antibody titers in the two study groups and study the relationship between endemic infections, IA, the FRCn, and CD4 and CD8 T cell subsets and the magnitude and durability of neutralizing antibody response to YFV in a cohort shown to have elevated IA, a damaged FRCn, and pan T cell depletion and a cohort that does not. This is a single arm, open-label, two cohort study of healthy adults in Kampala, Uganda and in Minnesota, USA. The cohort in Uganda will be 30 adults (15 men and 15 women) and the cohort in Minnesota will be 16 adults (8 men and 8 women). Everyone will be screened to ensure there are no contraindications to receiving YFV (e.g., immunosuppression) or the planned procedures. The inclusion and exclusion criteria are discussed in detail in the protocol that is included in the appendix. Participants will have an inguinal LN biopsy and leukapheresis prior to YFV and another LN biopsy 3 weeks after the vaccine administration. The vaccine will be given in the contralateral thigh from the first LN biopsy so that the second biopsy will be from a draining LN. PBMC and plasma will be collected at regular intervals over the 18-month follow-up period. Leukapheresis will be done again at the month 6 visit.

4.2 SCIENTIFIC RATIONALE FOR STUDY DESIGN

Our preliminary data shows that lymph node inflammation and damage to the FRCn correlates to peak titer. We also show data to suggest that there is significantly less LN damage from inflammation in native Minnesotans (not immigrants—we have not studied that). We think the differences are because of exposure to endemic infections. We will therefore use an open-label, non-randomized design to test our hypothesis.

4.3 JUSTIFICATION FOR DOSE

This is the standard of care dose of yellow fever vaccine.

4.4 END OF STUDY DEFINITION

A participant is considered to have completed the study if he or she has completed all phases of the study including the last visit or the last scheduled procedure shown in the Schedule of Activities (SoA), Section 1.3.

5 STUDY POPULATION

5.1 INCLUSION CRITERIA

Study entry is open to adults regardless of race or ethnic background. While there will be every effort to seek out and include minority patients from both genders, the patient population is expected to be no different from that of the populations in Minnesota and Kampala, Uganda.

In order to be eligible to participate in this study, an individual must meet all of the following criteria

1. Age ≥ 18 years but < 60 years
2. No contraindication to Yellow Fever vaccine (immunosuppressed for any reason or on an immunosuppressive drug where a live virus vaccine is contraindicated).
3. If female of childbearing age must agree to contraception for one month following administration of the vaccination.

5.2 EXCLUSION CRITERIA

An individual who meets any of the following criteria will be excluded from participation in this study

1. History of yellow fever or previous vaccination for yellow fever
2. Known bleeding disorder
3. Prior surgery complicated by clotting abnormality
4. Psychiatric or behavioral disorder that, in the opinion of the investigator, will make it difficult for the participant to complete the study
5. History of acute hypersensitivity reaction to any component of the vaccine (including gelatin, eggs, egg products, or chicken protein).
6. Thymus disorder associated with abnormal immune function
7. Immunosuppression from any of the following: HIV infection or AIDS, malignant neoplasms, primary immunodeficiencies, transplantation, transplantation, immunosuppressive or

immunomodulatory therapy (corticosteroids, alkylating agents, antimetabolites, TNF inhibitors, IL-1 blocking agents, monoclonal antibodies targeting immune cells), previous radiation therapy.

8. Pregnant or breastfeeding at the time of vaccination.
9. Planning to conceive within 28 days of enrollment and vaccination with the yellow fever vaccine.

5.3 LIFESTYLE CONSIDERATIONS

N/A

5.4 SCREEN FAILURES

Screen failures are defined as participants who consent to participate in the clinical trial but are not subsequently eligible to be entered in the study. A minimal set of screen failure information is required to ensure transparent reporting of screen failure participants, to meet the Consolidated Standards of Reporting Trials (CONSORT) publishing requirements and to respond to queries from regulatory authorities. Minimal information includes demography, screen failure details, eligibility criteria, and any serious adverse event (SAE).

5.5 STRATEGIES FOR RECRUITMENT AND RETENTION

In Minneapolis, Minnesota, participants will be recruited through the use of flyers via email, mail, and fax, study website, advertisements and primary care providers making information available to potential participants. In addition, the research team will work with the Fairview Uptown travel clinic to identify potential participants based on yellow fever vaccination appointments. In Kampala, Uganda recruiting will occur by referral from primary doctors and advertisements.

6 STUDY INTERVENTION

There are no study interventions and the following information is provided as they are central to the study. Stamaril and YF-VAX are the manufacturers and both can be used at either study site.

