6.1 STUDY INTERVENTION(S) ADMINISTRATION

6.1.1 STUDY INTERVENTION DESCRIPTION

YF-VAX® and Stamaril®, Yellow Fever Vaccine, for subcutaneous use, is prepared by culturing the 17D-204 strain of yellow fever virus in living avian leukosis virus-free (ALV-free) chicken embryos. The vaccine contains sorbitol and gelatin as a stabilizer, is lyophilized, and is hermetically sealed under nitrogen. No preservative is added. Each vial of vaccine is supplied with a separate vial of sterile diluent, which contains Sodium Chloride Injection USP – without a preservative. Stamaril is formulated to contain not less than 4.74 log₁₀ plaque forming units (PFU) per 0.5 mL dose throughout the life of the product. Before reconstitution, Stamaril is a pinkish color. After reconstitution, Stamaril is a slight pink-brown suspension. The vial stoppers for Stamaril and diluent are not made with natural rubber latex.

YF-VAX and Stamaril are approved for the prevention of yellow fever in persons 9 months of age and older.

Stamaril is an already licensed product in Uganda. It was approved by the National Drug Authority (NDA) under registration / reference number NDA/MAL/HDP/1482. The vaccine is manufactured by SANOFI PASTEUR in France and is distributed by Laborex (U) Limited in Uganda.

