6.1.2 DOSING AND ADMINISTRATION

YF-VAX and Stamaril are administered in a single subcutaneous injection of 0.5 mL of reconstituted vaccine.

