6.2 PREPARATION/HANDLING/STORAGE/ACCOUNTABILITY

6.2.1 ACQUISITION AND ACCOUNTABILITY

In Minnesota, the vaccine will be administered per the study's vaccine administration SOP at Park Nicollet Travel Clinic in St. Louis Park, MN, Fairview Uptown Travel Clinic in Minneapolis, MN, or any travel clinic that is authorized to administer the yellow fever vaccine. The travel clinician will indicate the vaccine administration site for study documentation.

In Uganda, the vaccine will be supplied from the commercial pharmacy and administered in the research clinic in a manner identical to what is described above in our background discussion.

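### Either vaccine product may be used at either site and no planned analysis looks at product, so product could be partly or wholly confounded with country in the primary comparison (minor, cheap to improve)

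*Combined protocol and SAP*

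**What the plan says.** Section 6 states that "Stamaril and YF-VAX are the manufacturers and both can be used at either study site". Nothing in the protocol standardises the choice.

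The supply routes in 6.2.1 differ. In Uganda "the vaccine will be supplied from the commercial pharmacy and administered in the research clinic". In Minnesota the vaccine is given under a study SOP at two named travel clinics "or any travel clinic that is authorized to administer the yellow fever vaccine". Section 5.5 adds that staff will work with one travel clinic "to identify potential participants based on yellow fever vaccination appointments". Section 6.1.1 notes that "Stamaril is an already licensed product in Uganda" and makes no matching statement for YF-VAX.

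The two products are described jointly. Section 6.1.1 says the vaccine "is prepared by culturing the 17D-204 strain of yellow fever virus", and 6.1.2 says that "YF-VAX and Stamaril are administered in a single subcutaneous injection of 0.5 mL of reconstituted vaccine". A potency floor is given for one product only: "Stamaril is formulated to contain not less than 4.74" log10 PFU per 0.5 mL dose.

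Section 9.4.2 compares peak titer between the US and Uganda by Mann-Whitney test, with stratification by gender. Section 9.4.7 allows further clinical factors in the models and gives age and demographics as examples. Neither these sections nor 9.4.3 or 9.4.9 names vaccine product.

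**The concern.** The cohorts being compared may not receive the same product, and the route that decides the product differs by country. If one product predominates in Kampala and the other in Minnesota, a difference in peak titer is a difference in country and product together.

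This does not touch the hypothesis in 9.1, which concerns only a US-Uganda difference. It touches the explanation. Section 3 expects lower titers because endemic infection has damaged lymphoid tissue. A product effect aligned with country could imitate part of that difference or hide part of it. Without product by participant, nobody could check. Country differs in many other ways that the study cannot control. Product is one that it can record and, in part, hold constant.

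**Working it through.** **Inputs from the documents (9.2, 9.4.2).** 30 Ugandans and 16 Minnesotans; SD 1 log in both; target difference 1 log; two-sided alpha 0.05; Mann-Whitney test.

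**Inputs assumed.** A product effect b of 0.1, 0.25 or 0.5 log, and several product splits. The documents give neither, so these values only illustrate a range.

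**Step 1: the plan's own power.** The standard error of the mean difference is sqrt(1/30 + 1/16) = 0.310 log. A noncentral t calculation with 43 df gives 0.884, against a stated figure of over 85%. Mann-Whitney simulation (20,000 runs) gives 0.866 for the normal case (stated 0.871) and 0.841 for the shifted t case (stated 0.841). The plan's figures reproduce.

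**Step 2: bias.** Bias in the mean contrast = b × (share on a given product in Uganda − share on it in Minnesota). For example, 30/30 v 8/16 gives a share difference of 1.00 − 0.50 = 0.50, so b = 0.25 gives a bias of about 0.12 log. For 22/30 v 4/16 the share difference is 0.733 − 0.250 = 0.483.

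**Step 3: false-positive rate with no true country effect** (normal data, 20,000 runs per cell).

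| Split, Uganda v Minnesota | Share difference | b = 0.1 | b = 0.25 | b = 0.5 (assumed worst case) |
|---|---|---|---|---|
| 30/30 v 0/16 | 1.00 | 0.056 | 0.115 | 0.323 |
| 30/30 v 8/16 | 0.50 | 0.051 | 0.064 | 0.109 |
| 22/30 v 4/16 | 0.483 | 0.050 | 0.061 | 0.106 |
| 30/30 v 12/16 | 0.25 | 0.050 | 0.053 | 0.062 |
| 15/30 v 8/16 | 0 | 0.047 | 0.045 | 0.040 |

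A separate run of the worst cell gave 0.327.

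**Step 4: power for a true 1-log difference when product acts against it.** Without a product effect, power is about 0.86. Under full alignment it is 0.788, 0.632 and 0.335 at b = 0.1, 0.25 and 0.5. With 30/30 v 8/16 it is 0.828, 0.759 and 0.618.

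**Step 5: what a same-product comparison could show.** Power for 1 log (asymptotic to exact Mann-Whitney) is 0.642 to 0.658 at 30 v 8, and 0.382 to 0.408 at 30 v 4. The approximate 95% half-width is 1.96 × sqrt(1/30 + 1/8) = 0.78 log at 30 v 8 and 1.96 × sqrt(1/30 + 1/4) = 1.04 log at 30 v 4. The full cohorts give 1.96 × 0.310 = 0.61 log. Such a comparison can describe, but it cannot settle the question.

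**The case against.** The strongest reply is that nothing in the documents suggests that the products differ in immunogenicity. Strain, culture method, volume and route are described as common to both. A missing potency figure for YF-VAX is silence, not evidence of a difference. An effect of 0.5 log is half of the plan's whole target difference and was picked for illustration. All of this stands. It limits the weight of the point, but it does not show that the two doses are equal.

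Alignment is also conjecture. A reader might infer that Ugandans will all receive Stamaril and Minnesotans YF-VAX. The documents do not say so. Section 6 permits both products at both sites, the Ugandan licensing statement is not a statement of what will be used, and no section says what the Minnesota clinics stock.

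A reader might also infer that product will go unrecorded. Section 6.2.1 mentions only the administration site as something that the travel clinician documents, and 10.1.8.1 does not list product among the data entered. But the vaccine administration SOP and the CRFs are not in the public documents and may already capture it. The open wording of 9.4.7 could admit product to the models, although it would not reach the primary Mann-Whitney test.

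Finally, the design is openly non-randomised, and removing product would not make the country contrast causal. That is true. It is a reason for modest weight, not for leaving a controllable factor unexamined.

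**Conclusion.** The point holds as a minor, cheap improvement. The text permits the product to differ between the two cohorts that the primary test compares, and no planned analysis would show whether it did. The size is unknown and may be nil. If product use is equal across countries, or the products perform alike, there is no bias. At an assumed 0.1 log the error rate stays near nominal. Only the assumed worst case, 0.5 log with complete alignment, reaches about a third. These figures rest on the plan's SD of 1 log, normal data, and product effects and splits that are not in the documents.

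Two stronger conclusions are not supported. The primary test is not invalid, because it answers the null that 9.1 states. Nor do the documents show that a US-Uganda difference would be due to product. What is at stake is how confidently a difference can be put down to endemic infection and lymph node damage.

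**What to change.** In sections 6 and 6.2.1, replace the open permission with one product at both sites where supply allows. Require product and lot to be recorded for each participant at Day 1, or cite the vaccine administration SOP if it already does this.

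In 9.4.2, tabulate product by country. Where one product is used in both countries, add a descriptive comparison of peak titer among its recipients, giving an estimate and interval and labelling it as low-powered so that a null result is not over-read. If no product is used in both countries, report the primary result as a combined country-and-product difference.

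The cost is two CRF fields at most, one table, one descriptive comparison and one reporting sentence. The primary test, sample size and alpha do not change. The downside is that standardising depends on local supply, and the same-product subset may be small or empty. Under full alignment no analysis can separate the two effects, and only the reporting limit applies.
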